8.5. Study Termination

The study will be completed as planned unless:

- New information or other evaluation regarding the safety of the study medication indicates a change in the known risk/benefit profile for the compound, such that the risk/benefit is no longer acceptable for participants participating in the study. This may be determined by the Sponsor, the Investigator, the IRB/IEC or regulatory authorities.
- The study is terminated by the Sponsor for administrative reasons.

The Sponsor, Investigator, the IRB/IEC, and the regulatory authority reserve the right to terminate or suspend the study at any time; however, termination or suspension of the study should be discussed between the relevant parties beforehand and the reason for such decision recorded. Should this occur, all data available will also be recorded in the eCRFs. If the Sponsor, the IRB/IEC, or regulatory authority elects to terminate or suspend the study or the participation of the investigational site, a study-specific procedure for early termination (ET) or suspension will be provided by the Sponsor. The procedure will be followed by the investigational site during termination or study suspension.

The Investigator should notify the relevant IRB/IEC and/or regulatory authority in writing of the study's completion or early discontinuation.

[figure not shown]
Figure 1: Study Design

Table 4: Schedule of Assessments

Assessment/Schedule	Screening	Treatment	Follow-up		
			Day 2	Week 2	Week 4
Day	-28 to -1	1*	2	15 ± 4 days	29 ± 4 days
Visit	1	2		3/ET	4/EOS (Telephone)
██████████	█				
██████████	█	█			
██████████	█				
████████████████████	█				
██████████████				█	█
██████████████					
██████████████	█	█			
██████████████	█	█	█	█	
██████████	█	█	█	█	
████	█	█		█	
██████████					
██████████	█	█		█	
██████████	█	█		█	
██████████████	█	█		█	
██████████████	█				
██████████████		█			
████████████████████		█	█		
████████████████████		█			
████	█	█	█	█	█
██████████████		█	█	█	█

Abbreviations: AE = adverse event; ECG = electrocardiogram; EOS = End of Study; ET = Early Termination; IP = investigational product; PK = pharmacokinetic.

Notes: *Available measurements of medical evaluations (body weight, abdominal subcutaneous fat thickness, physical examinations, and ECG) and laboratory evaluations (biochemistry, hematology, coagulation, and urinalysis) within 14 days prior to IP dose can be accepted as the Baseline value and will not necessitate duplicate examinations.

* [REDACTED]

[REDACTED]

9. SELECTION AND WITHDRAWAL OF PARTICIPANTS

9.1. Participant Inclusion Criteria

To be eligible for this study, a participant must meet **all** of the following inclusion criteria:

1. Male/female aged 18 years to 64 years old (at Screening), inclusive.
2. Body mass index (BMI) >18.5 and <35 kg/m² and body weight ≥ 50 kg at Screening and Day 1.
3. Participant has sufficient subcutaneous fat thickness of at least 3.00 cm (30.0 mm) measured by caliper skinfold method surrounding the center of localized area of treatment as well as the left and right edges of treatment area at Screening and Day 1.
4. Voluntarily signs the Informed Consent Form (ICF) and, in the opinion of the Investigator or delegate, is physically and mentally capable of participating in the study, and willing to adhere to study procedures, including food and drink restrictions.

9.2. Participant Exclusion Criteria

A participant who meets **any** of the following exclusion criteria must be excluded from the study:

1. Women of childbearing potential (WOCBP) who are not willing to commit to an acceptable contraceptive regimen from the time of Screening and throughout study participation until 90 days after the last IP dose, or who are currently pregnant or lactating. Male participants who are not willing to commit to an acceptable contraceptive method. For details on contraception, refer to [Section 9.3.3](#). Female participants who are not WOCBP are not required to use contraception.

* Not WOCBP is defined as females who have been surgically sterilized (hysterectomy or bilateral oophorectomy) or who are postmenopausal (defined as at least 50 years, with ≥ 12 months of amenorrhea) with a follicle-stimulating hormone (FSH) >40 IU/L prior to Screening.
2. Participant diagnosed with coagulation disorders or is receiving anticoagulant/antiplatelet therapy or medications or dietary supplements, which impede coagulation or platelet aggregation.
3. Participant has hemoglobin A1c (HbA1c) $\geq 9\%$, delayed wound healing, or any diabetic risks which, in the opinion of Investigator, is inappropriate to participate in the study.
4. Participant has a clinically significant cardiovascular disease and clinically significant abnormal findings in electrocardiogram (ECG).
5. Participant with active or prior history of malignancies within 5 years before Screening or being worked-up for a possible malignancy. Except adequately treated basal cell carcinoma of skin and in situ squamous cell carcinoma of skin would be eligible as per Investigator's discretion.

6. Participant with a history of human immunodeficiency virus (HIV)-1 infection, or participants with active HIV infection at Screening with positive HIV antigen/antibody (Ag/Ab) combo test.
7. Participants with any hepatic medical condition that, in the opinion of the Investigator, would compromise the participant's ability to undergo study procedures and/or interfere with the assessment of the obtained data.
8. Participants with a history of trypanophobia, the extreme fear of medical procedures involving injections or needles, or who experience vasovagal syncope and faint or pass out at the sight of blood or a needle.
9. Participant has abnormal skin or local skin conditions at the treatment area, which in the opinion of Investigator, is inappropriate to participate in the study, including but not limited to any of the following:
 - a. Skin manifestations of a systemic disease,
 - b. Cicatricial tissue or any abnormality of the skin or soft tissues on the anticipated treatment area,
 - c. Grade III cellulite (Nürnberg and Muller scale, [Nürnberg 1978](#)) at the area to be treated,
 - d. Skin folding on treatment area when the participant is in the supine position,
 - e. Sensory loss or dysesthesia in the area to be treated,
 - f. Evidence of any cause of enlargement in the area to be treated other than localized subcutaneous fat,
 - g. Tattoos on the area to be treated.
10. Participant who has the following procedures:
 - a. Previous surgery which caused scar tissues on the anticipated treatment area before Screening or during the study, except laparoscopic surgery and surgery which causes very small scar tissues would be eligible as per Investigator's discretion,
 - b. Liposuction to the region to be treated before Screening or during the study,
 - c. Esthetic procedure e.g., cryolipolysis, ultrasonic lipolysis, LLLT, lipolysis injection to the region to be treated within 12 months before Screening or during the study.
11. Participant is undergoing chronic systemic steroid or immunosuppressive therapy.
12. Requiring continual use of the following therapeutic agents during the study: terfenadine, buspirone, fexofenadine, any medication that is known to strongly inhibit or induce CYP enzymes (refer to [Section 24.1](#)), sensitive CYP substrates or drugs with narrow therapeutic index, in the opinion of the Investigator, may affect the evaluation of the study product or place the participant at undue risk.

If a participant needs to use the above-mentioned therapeutic agents during the study for any reason, these therapeutic agents should not be used for at least 2 days prior to dosing and until 1 day post-dose.
13. Unable to receive local anesthesia (e.g., history of hypersensitivity to lidocaine).
14. Participants with known allergies or sensitivities to the IP or its components.

15. Participants with liver cirrhosis or with inadequate liver function at Screening defined as aspartate aminotransferase (AST), alanine aminotransferase (ALT), alkaline phosphatase (ALP), total bilirubin (TBIL), or gamma-glutamyl transferase (GGT) $> 3.0 \times$ upper limit of normal (ULN).
16. Participants with any renal impairment, defined as abnormal serum creatinine, and urea $> 1.5 \times$ ULN or estimated glomerular filtration rate (eGFR) < 90 mL/min/1.73 m². Participants who are currently on dialysis should be excluded.

Participants with an eGFR ≥ 60 and < 90 mL/min/1.73 m² at Screening should be evaluated by the Investigator to exclude pre-existing renal disease or associated dysfunction. If mild decrease in eGFR is assessed by the Investigator as not clinically significant or not related to dysfunction, the subjects may be eligible upon the Investigator's assessment.
17. Use of other investigational drug or device within 4 weeks prior to Screening.

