Participants will remain in the clinic for at least 24 hours after dosing. During this time, blood samples will be collected to determine the PK and metabolites profile of curcumin and resveratrol. PK samples will be collected from all 10 participants. Of these 10 participants, 6 participants (the first 3 females and the first 3 males enrolled) will have additional samples collected for metabolite assessment.

Prior to discharge on Day 2, at the discretion of Investigator, participants may be prescribed analgesics and/or antihistamines to treat injection site reactions.

Follow-up will be performed at Week 2 and Week 4 to assess safety.

An Early Termination visit will be planned for any participant who receives treatment and is withdrawn from the study earlier than scheduled.

Participants who cannot meet the dosing compliance specified in [Section 10.5](#) will be withdrawn and will not continue the collection of PK samples post-dose. Safety assessment post-dose on Day 1 will be completed before discharge and an Early Termination visit will be planned.

Number of Participants:

10 (5 females and 5 males).

Inclusion Criteria:

A participant can participate in the study only if all the following criteria are met:

1. Male/female aged 18 years to 64 years old (at Screening), inclusive.
2. Body mass index (BMI) > 18.5 and $< 35 \text{ kg/m}^2$ and body weight $\geq 50 \text{ kg}$ at Screening and Day 1.
3. Participant has sufficient subcutaneous fat thickness of at least 3.00 cm (30.0 mm) measured by caliper skinfold method surrounding the center of localized area of treatment as well as the left and right edges of treatment area at Screening and Day 1.
4. Voluntarily signs the Informed Consent Form (ICF) and, in the opinion of the Investigator or delegate, is physically and mentally capable of participating in the study, and willing to adhere to study procedures, including food and drink restrictions.

Exclusion Criteria:

A participant who meets any of the following exclusion criteria must be excluded from the study:

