6.4. Participant Population

The study will be conducted in healthy male and female volunteers aged 18 to 64 years (inclusive at the time of informed consent) with a subcutaneous fat thickness of at least 3.00 cm (30.0 mm) measured by caliper skinfold method, surrounding the center of localized area of treatment as well as the left and right edges of treatment area at Screening and Day 1.

Women of childbearing potential (WOCBP) will be included and are subject to contraceptive requirements during the study from Screening until study completion, including the follow-up period, and for at least 90 days after the last dose of investigational product (IP) (see [Section 9.1](#)). WOCBP must demonstrate negative pregnancy testing at Screening and before

administration of IP. This is in line with regulatory Guidance on Nonclinical Safety Studies for the Conduct of Human Clinical Trials and Marketing Authorization for Pharmaceuticals (FDA 2006).

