8.4. Stopping Criteria

Administration of the IP may be paused, and additional participants will not receive IP, until a consultation has taken place between the Investigator, the MM, and the Sponsor representative under the following circumstances:

1. Any participant experiences an AE as Grade 3 (as defined in the NCI-CTCAE Version 5.0) for cardiovascular, renal or hepatic events considered to be at least possibly related to IP.
2. Except for cardiovascular, renal or hepatic events specified in Criterion #1, any participant experiences an AE as Grade 4 and considered to be at least possibly related to IP.

3. Any participant experiences a serious AE (SAE) that is considered to be at least possibly related to the IP.
4. An AE or group of AEs that singularly or in aggregate suggests to the Investigator or Sponsor that the IP is poorly tolerated and further treatment per protocol may not be safe.

If any of these criteria are met, consultation between the Sponsor representative, the Investigator, and the MM will take place as soon as possible to evaluate the event. Participants should remain in the study and be followed until the AE resolves or stabilizes.

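### Exclusion 4 joins cardiovascular disease and an abnormal ECG with 'and', so read literally neither alone excludes, and no other listed exclusion covers either one

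*Combined protocol and SAP*

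**What the plan says.** Section 9.2, criterion 4, reads "Participant has a clinically significant cardiovascular disease and clinically significant abnormal findings in electrocardiogram (ECG"). The Synopsis repeats it word for word, so neither place settles how the other should be read.

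The instruction for applying the list is "A participant who meets any of the following exclusion criteria must be excluded from the study". One criterion is therefore enough to exclude, and the logic inside criterion 4 decides whether that criterion is met.

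Section 6.4 describes the intended population: "The study will be conducted in healthy male and female volunteers aged 18 to 64 years". The study title also specifies healthy volunteers.

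Section 8.4 lets dosing be paused under several circumstances, the first being "Any participant experiences an AE as Grade 3 (as defined in the NCI-CTCAE Version 5.0) for cardiovascular, renal or hepatic events", if considered at least possibly related to the product. For other events the corresponding threshold is Grade 4.

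**The concern.** The conjunction makes criterion 4 a joint condition. Either finding alone leaves it unmet, although each alone is the kind of finding that a healthy-volunteer study would ordinarily be expected to screen for. What is at stake is consistent eligibility decisions. If the listed rule does not cover the case, the outcome depends on how each person at the site reads one word, or on general clinical judgement.

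The cardiovascular system is also one of three that the protocol watches more closely than the rest. The hepatic and renal systems each have an exclusion that a single finding can satisfy. The cardiovascular exclusion, as worded, needs two.

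**Working it through.** No figure in the plan is involved, so the check is one of logic and of reading the lists side by side.

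**Step 1: what criterion 4 does as written.** Let D be clinically significant cardiovascular disease and E be clinically significant abnormal ECG findings.

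| D | E | Literal reading (D and E) | Either/or reading (D or E) |
|---|---|---|---|
| yes | yes | excluded | excluded |
| yes | no | not excluded by criterion 4 | excluded |
| no | yes | not excluded by criterion 4 | excluded |
| no | no | not excluded | not excluded |

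The readings differ in 2 of 4 rows. The gap is symmetric: it concerns disease with a normal tracing and an abnormal tracing without a diagnosis alike.

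**Step 2: does another listed criterion cover the two middle rows?** The numbered criteria can be read in full in the Synopsis and in Sections 9.1 and 9.2.

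- Exclusion 2 begins "Participant diagnosed with coagulation disorders or is receiving anticoagulant/antiplatelet therapy" and extends to other medicines and supplements with those effects. It catches some cardiac patients through their treatment, but not cardiovascular disease as such.
- No other exclusion mentions cardiovascular disease or the ECG.
- Inclusion 4 requires that the person, "in the opinion of the Investigator or delegate, is physically and mentally capable of participating in the study". It is mandatory, but its content is a general judgement and it names no organ system.
- Section 9.6 allows removal for a medical condition at the Investigator's opinion. This too is discretionary.

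No listed criterion explicitly closes either row.

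**Step 3: how the list is worded elsewhere.**

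- Criterion 3 uses 'or' for separately sufficient conditions: "delayed wound healing, or any diabetic risks which, in the opinion of Investigator, is inappropriate to participate in the study".
- Criterion 15 opens "Participants with liver cirrhosis or with inadequate liver function at Screening", the latter defined by laboratory limits. This is the closest parallel, since it pairs a disease with a test result and joins them with 'or'.
- Criterion 16 points the other way. Its renal definition places 'and' between creatinine and urea and then 'or' before eGFR, so 'and' is not used strictly throughout the list.

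**Step 4: comparison with the stopping criteria.** Section 8.4 sets Grade 3 for cardiovascular, renal and hepatic events and Grade 4 for the rest. On entry, hepatic conditions are handled by criteria 7 and 15, and renal impairment by criterion 16, where a low eGFR alone suffices, subject to the Investigator's assessment between 60 and 90 mL/min/1.73 m². Criterion 4 is the only one for these three systems that literally needs two findings to coincide.

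**The case against.** The best defence is that 'and' is loose drafting for a list of two cardiac exclusions, and that nobody would apply it otherwise. Criterion 16 supports this. There are also real safeguards. Medical history is taken at Screening (Section 14.1.1), the complete physical examination covers the cardiovascular system (Section 14.1.5), and the Investigator or designee reviews every ECG tracing (Section 14.1.6). Wrongful entry would need an Investigator to call the condition clinically significant and still certify the person as fit under inclusion 4.

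Much of this stands, and it limits the consequence. It does not remove the defect. The safeguards are discretionary, and the word *healthy* in Section 6.4 is not a listed criterion. If the drafting is merely loose, the text still fails to state the intended rule.

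A reader might infer more than this, and the documents do not support it:

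- *That the protocol admits cardiac patients.* What is shown is that no listed exclusion covers the case, not that such a person would be enrolled.
- *That criterion 4 contradicts Section 6.4.* An incomplete exclusion list does not contradict a population description. Nor is *healthy* applied strictly here: the HbA1c cut-off is 9%, and liver tests exclude only above 3.0 × ULN. The fit is poor, which is a weaker statement.
- *That the dose aggravates the matter*, because 800 mg is 2.5 times the 320 mg reached in the Phase 1 study (800/320). The ratio says nothing about the conjunction. Sections 6.3 and 6.5 also make the dose subject to IRB/IEC review of interim safety data from CBL-0202, whose Stage 1 evaluates doses up to 800 mg.
- *That the safety results would be confounded.* This is a single-arm, descriptive study without hypothesis tests (Section 16). Laboratory, vital-sign and ECG data are reported with change from Baseline (Sections 16.4.2 to 16.4.4), so a pre-existing abnormality would be visible there.

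**Conclusion.** The point holds as a defect of wording in an operative eligibility rule. Read literally, criterion 4 is met only when both conditions are present, and no other listed exclusion covers either one alone. Only discretionary or unlisted safeguards would then keep such a volunteer out. This sits poorly with the healthy-volunteer population and with the attention that Section 8.4 gives to cardiovascular events.

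The size cannot be expressed as a number of participants, because the documents give no basis for estimating how many volunteers have one finding without the other. One participant would be 1/10 = 10% of the planned sample, but that is true of any eligibility question with 10 participants and measures nothing specific to this one. The sample size rests on no formal hypothesis test (Section 16.1), so no power or error-rate figure is touched.

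The conclusion assumes that sites apply the criterion as printed. That the sponsor intended either condition to exclude is plausible from criterion 15, but the text does not say so.

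**What to change.** State the intended logic of criterion 4 in the same words in the Synopsis and in Section 9.2, and reconcile it with the population described in Section 6.4. If either condition alone is meant to exclude, list them as two separate exclusions or join them with 'or', as criterion 15 does. If both together are meant, say so explicitly and explain how that agrees with a healthy-volunteer study.

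The cost is about one word in two places. Under the either/or wording there may be a few more screen failures. No analysis, endpoint or sample-size statement needs to change.

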9.3. Prohibitions and Restrictions in the Study

9.3.1. Medication

Concomitant use of the following medications, treatment modalities, or diets are prohibited during the study:

1. Use of anticoagulant/antiplatelet therapy or medications or dietary supplements which impede coagulation or platelet aggregation.
2. Any cosmetic or interventional surgery procedures on area to be treated.
3. Use of terfenadine, buspirone, fexofenadine, any medication that is known to strongly inhibit or induce CYP enzymes (please refer to [Section 24.1](#)), sensitive CYP substrates or drugs with narrow therapeutic index, in the opinion of the Investigator, may affect the evaluation of the study product or place the participant at undue risk.

If a participant requires the use of above-mentioned therapeutic agents during the study for any reason, these therapeutic agents should not be used at least for 2 days prior to dosing and until 1 day post-dose.

4. Use of other investigational drug or device within 4 weeks prior to Screening.

Participants should be advised not to take any prescription and over-the-counter (OTC) medications without consulting the Investigator.

9.3.2. Food and Drink Restrictions

During the study the foods and drinks outlined in [Table 5](#) should not be consumed 3 days prior to dosing until all PK samples have been collected.

Table 5: Food and Drink Restrictions During Study Participation

Type of food	Examples
Foods or supplements containing curcuminoids	Curry foods; supplements containing turmeric extracts or curcumin/curcuminoids
Foods or supplements rich in resveratrol	Red wines; red grapes (fruit and/or juice); chocolates; cocoa; peanuts
Alcoholic drinks	Beer; white wines

9.3.3. Contraception

Highly effective contraceptive methods with a failure rate of less than 1% per year when used consistently and correctly should be used. The list below is based on the recommendation of the Clinical Trial Facilitation Group (CTFG 2014).

- combined (estrogen and progestogen containing) hormonal contraception associated with inhibition of ovulation:
 - oral
 - intravaginal
 - transdermal
- progestogen-only hormonal contraception associated with inhibition of ovulation¹:
 - oral
 - injectable
 - implantable¹
- intrauterine device (IUD)¹
- intrauterine hormone-releasing system (IUS)¹
- bilateral tubal occlusion¹
- vasectomized partner^{1, 2}
- sexual abstinence³

¹ Contraception methods that in the context of this guidance are considered to have low user dependency.

² Vasectomized partner is a highly effective birth control method, provided that partner is the sole sexual partner of the WOCBP trial subject and that the vasectomized partner has received medical assessment of the surgical success.

³ In the context of this guidance sexual abstinence is considered a highly effective method only if defined as refraining from heterosexual intercourse during the entire period of risk associated with the study treatments. The reliability of sexual abstinence needs to be evaluated in relation to the duration of the clinical trial and the preferred and usual lifestyle of the subject. Periodic abstinence (calendar, symptothermal, post-ovulation methods) and withdrawal (coitus interruptus) are not acceptable methods of contraception. This is applicable for both female and male subjects.

- condom used by male partner during sexual intercourse.

Contraceptive requirements for male participants with WOCBP partner: A male participant should use condom during heterosexual intercourse and avoid sperm donation from the time of the first dose of IP, throughout study participation until 12 weeks after the last IP dose. For the WOCBP partner, contraception recommendations should also be considered.

